### **Selection and Recruitment of Participants:**

Approximately 15 evaluable subjects will be recruited from the Fontan clinic at CCHMC as well as the pediatric and adult congenital heart disease clinic at the University of Kentucky. Patients meeting eligibility criteria will be approached for participation during a regularly scheduled clinic visit at CCHMC. Alternatively, a letter of introduction approved by the IRB will be mailed to potential participants. In the letter, patients will be given the opportunity to opt-out of the study by calling the study line after receiving the letter. After one week, study personnel will call patients to further explain the study. If the patient's interest continues, study personnel will schedule a research visit for the patient at CCHMC. Written consent as outlined below will be obtained at their next clinic or study visit prior to any study procedures being conducted.

### **Inclusion/Exclusion Criteria**

#### **Inclusion criteria:**

- Underlying Fontan physiology
- On a stable medication regimen for the past 3 months
- Nine years of age or older

#### **Exclusion criteria:**

- Pregnant or nursing
- Prior hospitalization for heart failure in past year
- Presence of uncontrolled arrhythmias within the past 6 months
- Non-cardiac conditions which significantly limited exercise
- Moderate or severe ventricular dysfunction by echocardiogram or cardiac MRI
- Currently treated with a phosphodiesterase-5 inhibitor or organic nitrates
- Concurrent enrollment in other investigational drug trial
- End stage Liver Disease (ESLD)

### **Study Procedures/Interventions:**

Nearly all study procedures will occur at Cincinnati Children's Hospital Medical Center (CCHMC) main campus. The Heart Institute (HI) at CCHMC has an adult heart clinic where patients may be seen as well. The HI adult clinic is on site at the main hospital campus and therefore has full access to emergency medical staff onsite at the hospital.

The following procedures will occur during the study:

### **Baseline visit (Visit 1)**

- Informed Consent
- Baseline vitals (heart rate, blood pressure, oxygen saturation, height and weight)
- Demographic, medical, and medication review
- Urine pregnancy test for all females
- Blood collection (Basic Metabolic Panel-3ml)
- Insertion of peripheral venous cannula for venous blood pressure during exercise testing and estimate of mean capillary filling pressure
- Maximal cardiopulmonary exercise testing/Ramp protocol (including spirometry)
- Liver ultrasound to assess for liver stiffness
- Medication distribution

### **Visit 2 (3 days [+/-1 day] after Visit 1)**

- Follow-up phone call to ensure patient tolerating medication and adjust medications

### **Visit 3 (3 days [+/-1 day] after Visit 2)**

- Follow-up phone call to ensure patient tolerating medication and adjust medications

### **Visit 4 (3 days [+/-1 day] after Visit 3)**

- Follow-up phone call to ensure patient tolerating medication and adjust medications

### **Visit 5 (3 days [+/-1 day] after Visit 4)**

- Follow-up phone call to ensure patient tolerating medication and adjust medications if needed

### **Visit 6 (4 weeks after visit 3 [+/-2 days] before discontinuing ISDN)**

- Repeat vitals (heart rate, blood pressure, oxygen saturation, height and weight)
- Urine pregnancy test for all females
- Insertion of venous cannula for venous blood pressure during exercise testing and estimate of mean capillary filling pressure
- Maximal cardiopulmonary exercise testing/Ramp protocol (including spirometry)
- Liver ultrasound to assess for liver stiffness
- Recover medication vial
- Perform drug accountability
- Blood collection (Basic Metabolic Panel-3ml)

Table 1 presents schedule of procedures for this study.

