**2. To ensure low rate of side-effects in polypharmacy of Fontan patients**

### **Study Design:**

This will be a single arm, two-center prospective clinical trial of ISDN (up to 30 mg, 3 times daily) in pediatric and adult patients greater than 9 years old who have undergone the Fontan operation and do not have Fontan failure. The dose selected was based on current treatment protocols at the Cincinnati

Fontan clinic, literature review, and discussion with adult heart failure specialists. Fifteen patients will be enrolled from our Cincinnati Children's Fontan Clinic and collaborating pediatric cardiology clinic at the University of Kentucky. We will test the hypothesis that ISDN administration over 1-month period will be safely tolerated and improve exercise venous pressure responses, as well as exercise tolerance in Fontan patients. Our primary end point will be the change in exercise tolerance after 1 month of ISDN therapy. Secondary end points will include change in central venous pressure and cardiac output at rest and during exercise, mean capillary filling pressure, systemic blood pressure, heart rate, evidence of medication tolerance, and incidence of medication side effects including headaches.

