#### *Pharmacologic Interventions*

At the conclusion of the first visit ISDN therapy will begin at a small dose (5 mg three times daily in those targeting 20-30 mg TID, less in patients < 40 kg) and be titrated up to goal three times daily over 2 weeks (see Table 2). The medication will be continued for 4 weeks once the target dose is reached. It is an organic nitrate commonly used to prevent angina and used frequently in heart failure as well. It acts upon vascular smooth muscles to cause vasodilation of the peripheral arteries and veins. It should be taken by mouth three times per day with water. It may be taken with or without food.

Patients not tolerating the medication will be instructed to call the clinic for adjustment of medications. Severe side effects to note include pre-syncope, syncope, and severe headache. The PI will assess the patient over the phone and ask them to come in if necessary. Conversation and any changes of

medications will be documented. Less severe symptoms such as mild lightheadedness or headache should attempt to be tolerated or treated with acetaminophen prior to calling the clinic.

Isosorbide dinitrate's clinically relevant interaction is with phosphodiesterase-5 inhibitors, a common medication in Fontan patients. There is a risk for excessive hypotension and therefore, will be a contraindication to enrollment in the trial. ISDN can also affect kidney function. For this reason, a basic metabolic panel will be taken at the start of the study and 1 week after initiation of ISDN.

Side effects will attempt to be reduced by a step-wise up-titration plan, use of acetaminophen for headache, and recommendation to return to previous dose if necessary which may enhance tolerability. Furthermore, patients will be followed up with by phone call 3-5 days after any change in medication.

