#### **Proposed Dose**

ISDN will be administered by the CCHMC investigational pharmacy for a 2 week period of titrating up the dose followed by 4 continuous weeks of dosing of maximum tolerable dose determined by weight. Patients will be dispensed medication in 5mg, 10mg and 20 mg doses, and each patient will be given a personalized schedule for titrating up in dosage. Dosage may require halving a pill. See Table 2.

Patient Weight	<40 kg	40-49 kg	≥50 kg
Visit 1, Starting Dose	0.25 mg/kg/d	5 mg	5 mg
Visit 2, Up To	0.50 mg/kg/d	10 mg	10 mg
Visit 3, Up To	0.75 mg/kg/d	15 mg	15 mg
Visit 4, Clinic Visit, Up To	1.0 mg/kg/d	20 mg	20 mg
Visit 5, Up to		x	30 mg

Patients >50 kg will have a target dose of 30 mg TID. Patients 40-49 kg will have a target dose of 20 mg TID. Patients <40 kg will have a target dose of 1 mg/kg/d. Patients >40 kg will be started on low dose ISDN therapy (5 mg TID) at first to ensure they tolerate the medication. A phone call will be made 3-5 days after initiation of therapy to inquire about symptoms, and adherence to medication. If the patient is tolerating the medication well, the dose will be increased to 10 mg TID. Once increased, another follow-up phone call 3-5 days later will be made for further inquiry about the medication tolerance and increased to 15 mg TID. After 15 mg is reached patient will be brought in to clinic to check blood pressure and draw BMP and increase the dose. In patients ≥50 kg, dose will be increased once more to 30 mg TID. Once the patient dose is stable, it will be continued for a 4 week trial. If patients are symptomatic or not tolerating the medication at follow-up phone call, attempts will be made to adjust background medications prior to lowering the ISDN dose and follow-up phone calls will be made at 3-5 days after any adjustment to therapy.

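### Visit 6 is timed from Visit 3, before any weight group is at target dose, so a patient reaching 30 mg at Visit 5 has about 22 days on it (18–26), not 4 weeks

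*Combined protocol and SAP*

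**What the plan says.** Three statements in the dosing text start the 4 weeks at the final dose:

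- Pharmacologic Interventions: "The medication will be continued for 4 weeks once the target dose is reached".
- Proposed Dose: about 2 weeks of titration, then "4 continuous weeks of dosing of maximum tolerable dose determined by weight".
- Proposed Dose, later in the same section: "Once the patient dose is stable, it will be continued for a 4 week trial".

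The visit schedule starts them elsewhere. The heading for Visit 6 places it "4 weeks after visit 3 [+/-2 days] before discontinuing ISDN". Table 1 puts Visit 3 on Day 6 (±1) and Visit 6 on Day 34 (±3).

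The dose table under Proposed Dose sets these upper limits per visit:

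| Visit (nominal day) | <40 kg | 40–49 kg | ≥50 kg |
|---|---|---|---|
| Visit 3 (Day 6) | 0.75 mg/kg/d | 15 mg | 15 mg |
| Visit 4 (Day 9) | 1.0 mg/kg/d (target) | 20 mg (target) | 20 mg |
| Visit 5 (Day 12) | – | – | 30 mg (target) |

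For the heaviest group the text confirms the target: "Patients >50 kg will have a target dose of 30 mg TID".

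The endpoint wording in Study Design is looser: "Our primary end point will be the change in exercise tolerance after 1 month of ISDN therapy".

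**The concern.** Visit 6 carries the only follow-up exercise test and is where the drug is recovered. Its date therefore fixes the exposure behind the primary VO2 change. If the 4 weeks are counted from Visit 3, part of them is spent titrating for every patient who goes on to a higher dose.

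Three things are at stake.

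- **Following the protocol.** For a patient who reaches 30 mg at Visit 5, a site cannot obey both the dosing rule and the visit schedule. Table 1 shows drug dispensed only at Visit 1, so the supply has to be settled in advance on one reading or the other.
- **What the estimates describe.** The mean change and its SD are meant to inform the size of a confirmatory trial. A reader of the dosing section would take them to describe 4 weeks at the maximum tolerated dose. For patients who titrate past Visit 3 they describe less.
- **Uneven exposure.** Among patients of 50 kg or more, time at final dose falls as the tolerated dose rises. The Primary Objective covers the safety of a regimen titrated to the maximum tolerated dose or 30 mg, and Study Design lists evidence of medication tolerance as a secondary endpoint. Time at full dose bears on both.

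**Working it through.** **Inputs**

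- Visit 6 = Visit 3 + 28 days, ±2 (Visit 6 heading).
- Visit 4 is 3 ± 1 days after Visit 3, and Visit 5 is 3 ± 1 days after Visit 4 (visit headings).
- Nominal Days 6, 9 and 12 for Visits 3 to 5, each ±1, and Day 34 ± 3 for Visit 6 (Table 1).
- Calls or steps 3–5 days apart (Pharmacologic Interventions and Proposed Dose), used as a sensitivity case.
- The visit at which each weight group reaches target (dose table).

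**Step 1: reproduce the plan's Day 34.** 6 + 28 = 34. Earliest: 5 + 26 = 31. Latest: 7 + 30 = 37. This is exactly Table 1's Day 34 ± 3, so the Visit 3 anchor is built into both the text and the table. The ±2 and ±3 windows are consistent with each other.

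**Step 2: nominal days at final dose**, as 34 minus the day of the last dose step, for a patient of 50 kg or more:

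| Titration stops at | Dose | Days at final dose | Short of 28 |
|---|---|---|---|
| Visit 3 | 15 mg | 34 − 6 = 28 | 0 |
| Visit 4 | 20 mg | 34 − 9 = 25 | 3 |
| Visit 5 | 30 mg | 34 − 12 = 22 | 6 |

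The last shortfall is 6/28 = 21.4%. Patients under 50 kg who reach target do so at Visit 4 and also have 25 days.

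**Step 3: ranges over the windows**

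| Schedule | Visit 4 to Visit 6 | Visit 5 to Visit 6 |
|---|---|---|
| Visit headings (gaps of 2–4 days, Visit 6 anchored on Visit 3) | 26 − 4 = 22 to 30 − 2 = 28 | 26 − 8 = 18 to 30 − 4 = 26 |
| Visit headings and Table 1 windows together | 22 to 28 | 18 to 26 |
| Table 1 windows alone | 31 − 10 = 21 to 37 − 8 = 29 | 31 − 13 = 18 to 37 − 11 = 26 |
| Steps of 3–5 days, Visit 6 anchored on Visit 3 | 26 − 5 = 21 to 30 − 3 = 27 | 26 − 10 = 16 to 30 − 6 = 24 |

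Under each of these schedules, a patient who reaches 30 mg at Visit 5 falls short of 28 days. With the Visit 6 heading in force, a patient who finishes at Visit 4 reaches 28 days only if Visit 4 is 2 days after Visit 3 and Visit 6 is 2 days late.

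**Step 4: dates the dosing rule would require.** Last step at Visit 4: 9 + 28 = Day 37, the final day of the present window. Last step at Visit 5: 12 + 28 = Day 40, outside Days 31–37.

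**The case against.** **The endpoint is still met.** The Primary Objective speaks only of a 4-week regimen, and the endpoint and analysis text of one month of therapy. Day 34 fits that wording. The study is a single-arm pilot of 15 that estimates a mean change and an SD. It plans no analysis by dose or duration, and nothing in the documents says that the response depends on 28 rather than 22 days at final dose. All of this stands, and it limits the weight of the point. It does not reconcile the two rules, because the dosing sections say explicitly where the 4 weeks begin.

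**Mixing windows can reach 28 days.** Under the visit headings, Visit 5 could fall as early as 4 × 2 = Day 8. Paired with Table 1's latest Visit 6, that gives 37 − 8 = 29 days. But such a patient had Visit 3 on Day 4, so Visit 6 could be no later than Day 4 + 30 = 34, leaving 26 days. Day 8 is also outside Table 1's Days 11–13 for Visit 5. The pairing therefore breaks the plan's own rules. For patients finishing at Visit 4, Table 1 alone does allow up to 29 days, but the Visit 6 heading applies too and caps it at 28.

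**The dosing text could be changed instead.** One could keep Day 34 and state that time at final dose is roughly 3 to 4 weeks. This preserves a single assessment day and adds no exposure. Moving Visit 6 makes total time on drug rise with dose (34, 37 or 40 days), which is also an imbalance. This is a fair alternative. Moving the visit is preferable because the protocol states three times that it wants 4 weeks at the final dose.

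**Conclusion.** The concern holds. The visit schedule and the dosing rule contradict each other, and no other text in the protocol resolves it. A patient reaching 30 mg at Visit 5 has a nominal 22 days there: 18–26 with the stated windows, 16–24 with steps of 3–5 days. A patient finishing at Visit 4 has 25 (22–28, or 21–27). A patient who stabilises at Visit 3 has the nominal 28, so the problem is confined to those who titrate past Visit 3.

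These figures assume that titration follows the dose table without delays and that Visit 6 is timed from Visit 3 as written. The documents do not say how many patients will reach 30 mg, and they give no basis for estimating the effect on the VO2 mean change or SD. The primary analysis remains defined. The schedule should be corrected, but the point does not invalidate the study.

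**What to change.** In the Visit 6 heading and Table 1, set Visit 6 at 28 days (±2) after the participant's last dose increase, or after the date the dose becomes stable if it is later reduced. Nominally this is:

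- Day 34 for those stabilising at Visit 3 (unchanged);
- Day 37 for those finishing at Visit 4;
- Day 40 for those reaching 30 mg at Visit 5.

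Report each participant's final dose and days at that dose next to the VO2 change, so that the remaining differences in exposure are visible.

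**Cost.** The wording of the Visit 6 heading and Table 1 changes, and the visit falls 3 or 6 days later for the affected patients. Extra drug per patient is about 3 days × 60 mg = 180 mg at 20 mg TID, and 6 days × 90 mg = 540 mg at 30 mg TID; the supply dispensed at Visit 1 must allow for it. Visit 6 is no longer one fixed study day, and total time on drug varies with the titration step. No new procedure is needed.

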**Table 1: Patient Timeline**

	Visit 1	Visit 2	Visit 3	Visit 4	Visit 5	Visit 6
	Day 0	Day 3 (+/-1 day)	Day 6 (+/-1 day)	Day 9 (+/-1 day)	Day 12 (+/-1 day)	Day 34 (+/- 3 days)
Procedures:						
Informed consent	X					
Demographics and medical history	X					
Medication review	X					
Vital signs	X					X
Urine Pregnancy Test	X					X
Venous pressure a	X					X
Spirometry b	X					X
Maximal exercise ramp test	X					X
Liver Ultrasound	X					X
Quality of Life Survey	X					X
Medication dispensation	X					
Phone call to adjust medications		X	X	X	X	
Collect medication vial						X
Basic Metabolic Panel	X					X
Adverse event monitoring	X	X	X	X	X	X

a Venous pressure will be measured from before exercise test, every 1 minute during exercise, until 5 minutes after exercise.

b Spirometry will occur prior to maximal exercise testing

#### *Pharmacologic Interventions*

At the conclusion of the first visit ISDN therapy will begin at a small dose (5 mg three times daily in those targeting 20-30 mg TID, less in patients < 40 kg) and be titrated up to goal three times daily over 2 weeks (see Table 2). The medication will be continued for 4 weeks once the target dose is reached. It is an organic nitrate commonly used to prevent angina and used frequently in heart failure as well. It acts upon vascular smooth muscles to cause vasodilation of the peripheral arteries and veins. It should be taken by mouth three times per day with water. It may be taken with or without food.

Patients not tolerating the medication will be instructed to call the clinic for adjustment of medications. Severe side effects to note include pre-syncope, syncope, and severe headache. The PI will assess the patient over the phone and ask them to come in if necessary. Conversation and any changes of

medications will be documented. Less severe symptoms such as mild lightheadedness or headache should attempt to be tolerated or treated with acetaminophen prior to calling the clinic.

Isosorbide dinitrate's clinically relevant interaction is with phosphodiesterase-5 inhibitors, a common medication in Fontan patients. There is a risk for excessive hypotension and therefore, will be a contraindication to enrollment in the trial. ISDN can also affect kidney function. For this reason, a basic metabolic panel will be taken at the start of the study and 1 week after initiation of ISDN.

Side effects will attempt to be reduced by a step-wise up-titration plan, use of acetaminophen for headache, and recommendation to return to previous dose if necessary which may enhance tolerability. Furthermore, patients will be followed up with by phone call 3-5 days after any change in medication.

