#### **Potential Risks, Discomforts and Inconveniences:**

Potential risks, discomforts and inconveniences of this study include three office visits, two of which will require time and for the patient to undergo intravenous blood pressure measurement. Two of the visits will also require blood draw with similar risks. IV insertion could result in minimal bleeding, bruising and pain in a small portion of people. Furthermore, they will undergo exercise testing at two of these office visits, which is associated with arrhythmias in some patients and/or discomfort.

The risk associated with the medication, isosorbide dinitrate, are primarily due to hypotension which could lead to mild headaches or potentially severe systemic hypotension. Patients will be informed of this potential complication and instructed to contact the office and seek medical attention immediately for any syncopal or pre-syncopal events. Nitrate headaches are a common effect of ISDM and can often be controlled with aspirin or acetaminophen. Such adverse events are dose-related with a low incidence and occur more commonly in the elderly. They will also be told to have the patient lie down and elevate all four extremities to increase central pooling of blood. In the event of any severe reactions, the medication would be decreased to previously tolerated dose or stopped. Furthermore, this is a primary reason for the 3-5 day follow-up phone call. In Fontan patients, lowering blood pressure could also compromise kidney function which is why a 2 week follow-up visit will be performed to assess for any

significant changes to blood pressure at the discretion of the principal investigator based on patient baseline and normal blood pressure readings.

Patients under 18 having a positive pregnancy test will have the results reported to their parents and/or legal guardian. To mitigate the emotional risk from receiving a positive pregnancy result, study staff will offer chaplain services and/or a referral to counseling services. Lastly, there is a potential loss of confidentiality by participating in the study.

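### The text requires an on-drug blood pressure and metabolic panel check before Visit 6, at three different times, but Table 1 and the visit list contain none of them

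*Combined protocol and SAP*

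**What the plan says.** Drug starts on Day 0, per Pharmacologic Interventions: "At the conclusion of the first visit ISDN therapy will begin at a small dose". Potential Risks, Discomforts and Inconveniences describes the drug's risks as "primarily due to hypotension which could lead to mild headaches or potentially severe systemic hypotension" and adds that lower blood pressure may harm the kidneys.

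Three sections require a check on drug before the final visit:

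- Pharmacologic Interventions: "a basic metabolic panel will be taken at the start of the study and 1 week after initiation of ISDN".
- Proposed Dose: "After 15 mg is reached patient will be brought in to clinic to check blood pressure and draw BMP and increase the dose". The dose table there labels the row "Visit 4, Clinic Visit, Up To", and that row applies to all three weight bands.
- Potential Risks: "a 2 week follow-up visit will be performed to assess for any" significant change in blood pressure. This section counts three office visits, yet also says "Two of the visits will also require blood draw with similar risks".

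The operational sections leave no place for such a check. The visit list makes Visit 4 a follow-up phone call. Table 1 marks vital signs and the basic metabolic panel at Visits 1 and 6 only, and a phone call at Visits 2 to 5. Venous puncture places the panel at Visits 1 and 6. The Abstract has patients attending clinic twice, and Participation Cost and Payments covers two visits.

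**The concern.** Sites usually run a study from the schedule table and visit list. Here those would lead a site to omit a safety check that three other sections require. A site working from Proposed Dose would instead bring the patient in at about Day 9, before the last dose increases. Because the three stated times differ, a site also cannot tell whether one, two or three checks are intended.

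At stake is monitoring of the two effects the protocol itself identifies, low blood pressure and loss of renal function, during titration in patients as young as nine. Safety is part of the primary objective. With 15 patients at two centers, on-drug values collected in some patients and not in others would be hard to summarize for the DSMB. No phone call is described as obtaining a blood pressure or a laboratory value.

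**Working it through.** **Inputs**

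- Table 1: Visit 1 Day 0; Visits 2 to 5 on Days 3, 6, 9 and 12 (each ±1); Visit 6 on Day 34 (±3).
- Visit list: Visits 2 to 5 each 3 days (±1) after the one before; Visit 6 four weeks after Visit 3.
- Dose table: 15 mg (0.75 mg/kg/d below 40 kg) at Visit 3; target dose at Visit 4 below 50 kg and at Visit 5 for 50 kg or more.
- Payments: $50 per visit plus $100 for calls, $200 in total. Planned enrollment is 15.
- Assumption: every step is tolerated and taken on its Table 1 day.

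**1. The plan's own figure.** Visit 3 plus four weeks: 6 + 28 = Day 34, as in Table 1.

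**2. First on-drug check, by section followed**

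| Section | Blood pressure | Panel |
|---|---|---|
| Pharmacologic Interventions | not stated | Day 7 |
| Proposed Dose | Day 9 | Day 9 |
| Potential Risks | Day 14 | not stated |
| Table 1 | Day 34 | Day 34 |
| Venous puncture | not stated | Day 34 |

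**3. Could one visit meet all three requirements?**

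- Table 1 window for Visit 4: Days 8 to 10. This holds neither Day 7 nor Day 14.
- Visit-list windows added up: 3 × 2 = 6 to 3 × 4 = 12. This holds Day 7 but not Day 14.
- Calls every 3 to 5 days: 3 × 3 = 9 to 3 × 5 = 15. This holds Day 14 but not Day 7.

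Read literally, no single visit satisfies both the 1-week and the 2-week statements.

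**4. Days at target dose before Visit 6**

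- Below 50 kg: 34 − 9 = 25 (windows: 31 − 10 = 21 to 37 − 8 = 29).
- 50 kg or more: 34 − 12 = 22 (windows: 31 − 13 = 18 to 37 − 11 = 26).

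If Visit 6 instead followed four full weeks at target, as the dosing text has it, it would fall on 9 + 28 = Day 37 or 12 + 28 = Day 40. The figures here keep Table 1's Day 34.

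**5. Effect of a Visit 4 check**

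- First scheduled on-drug check: Day 34 becomes Day 9.
- Scheduled on-drug checks: 1 becomes 2.
- Longest interval without either value: 34 days becomes max(9, 34 − 9) = 25 days.
- Days at target without a required value: still 25 or 22.

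A Day 14 visit would fall 14 − 9 = 5 or 14 − 12 = 2 days after target is reached.

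**6. Draws and payment.** Blood draws are 2 under Venous puncture and Potential Risks, and 3 once the Proposed Dose panel is counted. Payment is now 2 × 50 + 100 = $200; with a third visit it is 3 × 50 + 100 = $250. Across 15 participants the addition is 15 × 50 = $750.

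**The case against.** The strongest reply is that the earlier check is already mandatory. All three sections use binding language, so a site that skips the check follows Table 1 but not the protocol. This stands. A reader might infer that the protocol allows blood pressure and panel to go unrepeated until Day 34; it does not. Day 34 is what the schedule sections produce by themselves.

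A second reply is that this is one titration visit loosely described. That is plausible as to intent, since the accumulated windows can bring Visit 4 near either one week or two. But the visit is absent from the schedule whichever time was meant.

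A third is that other safeguards exist. Dose increases depend on tolerance at each call, the investigator can bring a patient in, and for severe reactions "In the event of any severe reactions, the medication would be decreased to previously tolerated dose or stopped". Statistical Analyses has safety laboratory values monitored and reported to the DSMB, whose charter is not among the documents and may say more. These reduce the risk. But the calls and dose reductions act on symptoms, and the laboratory statement does not say when values are taken.

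A fourth is that a Visit 4 check precedes target dose, so it leaves time at target as it was, and moving the 2-week visit to Visit 4 gives up the one described check that would fall at target under Table 1 timing. This is correct and limits what the fix can claim.

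Finally, no planned analysis uses a Visit 4 value. Safety is reported as event counts, and blood pressure is compared between first and final visits. The matter is therefore safety monitoring, not bias in an estimate.

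**Conclusion.** The contradiction is real and should be corrected. Three sections require an on-drug check at nominal Days 7, 9 and 14; the schedule first provides one at Day 34 (31 to 37). Scheduling it at Visit 4 brings the first check forward by 34 − 9 = 25 days, ahead of the last dose increases. These figures assume titration on Table 1 days without delay. They are monitoring intervals, not event rates: the documents give no rate of hypotension or renal change, so no number of patients harmed can be derived.

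A reader might also infer that starting drug at the end of Visit 1 is itself a defect, because no section requires that day's blood pressure and panel to be reviewed first. The documents do not support going that far. Vital signs come before drug distribution in the Visit 1 list, a treating investigator would ordinarily see the results, the first dose is low, and no section states a blood pressure or renal limit that such a review would apply. It is not part of this point.

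**What to change.** Make Visit 4 (about Day 9) a clinic visit with blood pressure and a basic metabolic panel, done before any increase above 15 mg three times daily, or above 0.75 mg/kg/d in patients under 40 kg. Enter it in Table 1, the Visit 4 entry of the visit list, and Venous puncture. Then align the remaining sections:

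- Abstract: three clinic visits.
- Pharmacologic Interventions: replace the 1-week panel with Visit 4.
- Potential Risks: replace the 2-week visit with Visit 4, and change two blood draws to three.
- Participation Cost and Payments: three paid visits.

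If the sponsor also wants a value at target dose before Visit 6, that needs a separate later check; this change does not supply it.

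Cost: amendment wording and one clinic visit that Proposed Dose already calls for. At the current rate this adds $50 per participant, at most $750 for 15; the payment section mentions only participants from Cincinnati Children's. Kentucky patients would need to travel or have a local check, for which the documents give no cost. Study Procedures says nearly all procedures, not all, take place in Cincinnati, so a local check is not ruled out. Sample size and planned analyses do not change.

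### The visit schedule omits the phone call that the protocol's own rule requires 3-5 days after the step to 30 mg three times daily

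*Combined protocol and SAP*

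**What the plan says.** The follow-up rule is in Pharmacologic Interventions: "patients will be followed up with by phone call 3-5 days after any change in medication". It has no exception for the last step.

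The titration is in Proposed Dose and Table 2. For patients of 50 kg or more, the table gives 5, 10, 15, 20 and 30 mg at Visits 1 to 5, and the text says: "In patients ≥50 kg, dose will be increased once more to 30 mg TID". Patients of 40-49 kg stop at 20 mg and those under 40 kg at 1 mg/kg/day. Both reach target at Visit 4.

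Visit 5 is itself a call: "Follow-up phone call to ensure patient tolerating medication and adjust medications if needed". Table 1 marks the row "Phone call to adjust medications" at Visits 2 to 5 only (Days 3, 6, 9 and 12). The next column is Visit 6 on Day 34, which the visit list defines as "4 weeks after visit 3 [+/-2 days] before discontinuing ISDN". The adverse event row of Table 1 also has no entry between Day 12 and Day 34.

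Proposed Dose also says that "follow-up phone calls will be made at 3-5 days after any adjustment to therapy", but that sentence is conditional on a patient having symptoms or not tolerating the drug. Only the Pharmacologic Interventions sentence states the rule without a condition.

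**The concern.** The Visit 5 call checks tolerance of 20 mg and starts 30 mg, so it cannot also be the check on 30 mg. The one level without a scheduled early contact is therefore the highest dose. It is also reached by the largest absolute step: 10 mg per dose, against 5 mg at each earlier step.

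The primary objective includes the safety of a regimen taken to the maximal tolerated dose or 30 mg, so tolerance at 30 mg is central. The Potential Risks section calls the adverse effects dose-related, though of low incidence, and gives severe reactions as a main reason for the 3-5 day call.

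If the call is missed, two kinds of information would rest on recall at Visit 6: mild events that were never phoned in, which patients are told to tolerate or treat with acetaminophen first, and dose reductions that patients make themselves and do not report. Side-effect incidence, including headache, is a secondary end point in Study Design, and Statistical Analyses reports safety as event counts. Missed mild events could lower those counts.

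**Working it through.** **Inputs.** Table 1: Visit 3 on Day 6, Visit 4 on Day 9, Visit 5 on Day 12 (each ±1 day) and Visit 6 on Day 34 (±3 days). Visit list: each call 3 ±1 days after the one before, and Visit 6 at 4 weeks ±2 days after Visit 3. Table 2: the dose at each visit. Pharmacologic Interventions: call at 3-5 days.

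**1. Reproduce the plan's day for Visit 6.** Day 6 + 28 = Day 34, which agrees with Table 1.

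**2. Scheduled contact after each dose level (50 kg or more).**

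| Dose, three times daily | Started | Next contact | Nominal gap |
|---|---|---|---|
| 5 mg | Visit 1 | Visit 2 | 3 - 0 = 3 days |
| 10 mg | Visit 2 | Visit 3 | 6 - 3 = 3 days |
| 15 mg | Visit 3 | Visit 4 | 9 - 6 = 3 days |
| 20 mg | Visit 4 | Visit 5 | 12 - 9 = 3 days |
| 30 mg | Visit 5 | Visit 6 | 34 - 12 = 22 days |

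**3. The 30 mg gap with windows.**
- Table 1: shortest 31 - 13 = 18 days; longest 37 - 11 = 26 days.
- Visit list: Visit 3 to Visit 5 is 4-8 days and Visit 3 to Visit 6 is 26-30 days, so the gap is 26 - 8 = 18 to 30 - 4 = 26 days.

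Both sources give 18-26 days. Even 18 is far beyond 5, so Visit 6 cannot serve as the required call.

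**4. Dependence on the Visit 6 anchor.** Pharmacologic Interventions and Proposed Dose promise four weeks at the target dose. For a patient reaching 30 mg on Day 12 that means Day 12 + 28 = Day 40, and a gap of 28 days. The 22-day figure holds if Day 34 governs; under the other rule the gap is longer.

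**5. Comparison with lighter patients.** They reach target at Visit 4 and are called at Visit 5, 3 days later (2-4 with the visit-list window). The quiet period from Day 12 to Day 34 is common to all weight groups and is not the problem. What differs is whether the target dose has been checked before it begins.

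**6. Effect of adding the call.** It falls on Day 12 + 3 = 15 to Day 12 + 5 = 17 (Day 14-18 with the Visit 5 window). The first check at 30 mg comes 22 - 5 = 17 to 22 - 3 = 19 days sooner. The time then left to Visit 6 is 34 - 17 = 17 to 34 - 15 = 19 days, shorter than the 22 days that lighter patients have after their last call.

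**7. Could the two-week visit fill the gap?** Potential Risks mentions a two-week follow-up visit for blood pressure. Neither Table 1 nor the visit list shows it, and it may be the clinic visit that Table 2 places at Visit 4. If it took place on Day 14, it would fall 14 - 13 = 1 to 14 - 11 = 3 days after Visit 5, reaching 3 days only when Visit 5 is on Day 11. It cannot be relied on as the 3-5 day contact.

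**The case against.** The strongest reply is that the protocol already requires the call. The rule covers any change in medication, and Table 1 does not forbid a call on which it is silent. Table 1 is plainly not a full list of contacts: it also leaves out the clinic blood pressure check and metabolic panel that Proposed Dose requires once 15 mg is reached. It contains no doses, so staff must consult the dosing text to raise anyone to 30 mg. Proposed Dose adds that "each patient will be given a personalized schedule for titrating up in dosage". Patients who do not tolerate the drug are told to phone, the investigator assesses them, and resulting changes are documented. Adverse events are recorded from the first dose onward.

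Most of this stands, and it keeps the point minor. It does not remove it. The personalized schedule concerns upward titration and is not said to add follow-up contacts. Phoning in captures clinic-directed changes and troublesome symptoms, but not mild events or self-reductions that a patient does not report.

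It is also fair to say that the other contacts do not match the rule exactly. A window of 3 ±1 days permits a call on the second day, short of the 3-5 days required. But those levels do have an early contact, and 30 mg has none.

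Three stronger readings are tempting. A reader might infer that the protocol has no safeguard at the top dose, or that the schedule overrides the rule. Neither follows, because the rule is unconditional and the schedule merely omits the call. A reader might also infer that the VO2 result is compromised. The documents support only an indirect route, through unreported dose reductions before the Visit 6 exercise test, and that effect is likely small.

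**Conclusion.** The point holds as an omission in the schedule: Table 1 and the visit list do not implement the protocol's own follow-up rule at the 30 mg step. It amounts to one missing scheduled call per patient raised to 30 mg. The first scheduled check at that dose comes after 22 days (18-26 with windows, about 28 if four weeks at target sets Visit 6), against about 3 days at every lower level.

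This assumes that the 30 mg step is taken at Visit 5, as Table 2 shows, and applies only to patients who take it. The number weighing 50 kg or more is not stated, so among 15 patients it could be anywhere from 0 to 15. The number of events that would be missed cannot be estimated from the documents. Severity is minor.

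**What to change.** Add to Table 1 and the visit list a phone call 3-5 days after the Visit 5 increase (Day 15-17 when Visit 5 is on Day 12) for patients stepped to 30 mg three times daily. At that call, record adverse events, the dose actually taken and adherence, and go back to the previous dose if 30 mg is not tolerated.

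The cost is about one call per patient stepped to 30 mg, roughly 15 at most given the planned enrolment of approximately 15 evaluable patients. The rule already requires these calls. No clinic visit or procedure is added and Visit 6 does not move.

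If the sponsor also wants to align the Visit 2-5 windows with 3-5 days, Visit 6 should be re-anchored to the date the target dose is reached. With Visit 6 left at 28 ±2 days after Visit 3, the interval from Visit 3 to Visit 5 would become 6-10 days, and the minimum time at 30 mg would fall from 26 - 8 = 18 to 26 - 10 = 16 days.
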